14.0 STATISTICAL CONSIDERATIONS

A maximum of 48 patients will be enrolled in this Phase II study. Cohort 1 will enroll up to 24 CLL patients who are refractory to or have relapsed after at least one prior therapy; cohort 2 will enroll up to 24 untreated CLL patients with high-risk molecular features such as del(17p), mutated *TP53*, del(11q), unmutated *IGHV* gene, or are >65 years of age. The primary objective is to evaluate overall response (OR) during the first 6 months of therapy. The primary efficacy endpoint, overall response (OR), is defined as CR, CRi or PR that occurs during the first 6 months of therapy.

EFFICACY

For cohort 1, the target overall response rate is 30%. The Bayesian approach of Thall, Simon, Estey will be implemented for the futility monitoring.³¹ The following futility stopping rule will be applied in cohort size of 3, starting from the 9th patient: $\text{prob}\{p(\text{OR}) > 0.3\} < 0.05$, where $p(\text{OR})$ denotes the overall response rate. That is, the trial will be stopped early due to futility, if during the study we determine that there is less than 5% chance that the OR is more than 30%. Assuming that the prior distribution of $p(\text{OR})$ is beta (0.6, 1.4), the stopping boundaries corresponding to this futility monitoring rule are shown below in Table 14.1. The operating characteristics (OCs) for this futility stopping rule are summarized in Table 14.2.

Table 14.1. Futility stopping boundaries for cohort 1, in cohort size of 3.

Number of patients	Stop the trial if there are this many patients achieving OR
9	0

12-15	0-1
18	0-2
21	0-3

Table 14.2. Operating characteristics for the monitoring of OR rate in cohort 1.

True OR Rate	Early Stopping Probability	Average number of patients treated
0.1	0.88	13.8
0.2	0.45	19.4
0.3	0.14	22.6
0.4	0.03	23.7
0.5	0.005	23.9

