For cohort 2, the OR rate is ~30% with Rituximab and we target to reach an OR rate of 50% with the combination therapy. The same Bayesian approach of Thall, Simon, Estey will be implemented for the futility monitoring.³¹ The following futility stopping rule will be applied in cohort size of 3, starting from the 9th patient: $\text{prob}\{p(\text{OR}) > 0.3 + \delta\} < 0.05$, where $p(\text{OR})$ denotes the response rate and $\delta = 0.2$. That is, the trial will be stopped early due to futility, if during the study we determine that there is less than 5% chance that the OR rate with the combination therapy will improve from 30% (Rituximab alone) to 50%. Assuming that the prior distribution of $p(\text{OR})$ is beta (0.6, 1.4), the stopping boundaries corresponding to this futility monitoring rule are shown below in Table 14.3. The operating characteristics (OCs) for this futility stopping rule are summarized in Table 14.4.

Table 14.3. Futility stopping boundaries, in cohort size of 3, for cohort 2.

Number of patients	Stop the trial if there are this many patients achieving OR
9	0-2
12	0-3
15	0-4
18	0-5
21	0-7

Table 14.4. Operating characteristics for monitoring of OR rate in cohort 2.

True OR Rate	Early Stopping Probability	Average number of patients treated
0.2	0.97	11.0
0.3	0.78	14.8
0.4	0.44	19.1
0.5	0.16	22.2

0.6	0.04	23.5
0.7	0.005	23.9

TOXICITY

The Bayesian approach of Thall, Simon, Estey will be implemented for toxicity monitoring for patients enrolled in cohorts 1 and 2, where toxicity is defined as any grade 3 or higher non-hematological toxicity which is at least possibly related to the treatment.³¹ The toxicity, denoted as TOX will be monitored by the Bayesian stopping boundaries calculated based on beta-binomial distributions. We assume as a priori, $p(\text{TOX}) \sim \text{beta}(0.6, 1.4)$. The study will be stopped for toxicity if $\Pr(p(\text{TOX}) > 0.30 \mid \text{data}) > 0.92$. That is, we will stop the trial for new patient enrollment if at any time during the study we determine that there is more than 92% chance that the toxicity rate is more than 30%. The toxicity monitoring rule will be applied starting from the 6th patient, and then in cohort size of 6. The toxicity will be considered continuously throughout the study treatment duration. Stopping boundaries corresponding to this toxicity monitoring rule are shown in Table 14.5 below. The operating characteristics for toxicity monitoring are summarized in Table 14.6.

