Table 14.5. Toxicity stopping boundaries in cohort size of 6 for patients enrolled in cohorts 1 and 2.

Number of patients	Stop the trial if there are this many patients having toxicity
6	4-6
12	7-12
18	9-18
24	11-24
30	13-30
36	15-36
42	18-42

Table 14.6. Operating characteristics for toxicity monitoring.

True Toxicity Rate	Early Stopping Probability	Average number of patients treated
0.1	0.001	47.9
0.2	0.02	47.1
0.3	0.19	42.3
0.4	0.61	30.5
0.5	0.93	18.2

ANALYSIS PLAN

Summary statistics will be provided for continuous variables. Frequency tables will be used to summarize categorical variables. The overall response (OR) rate will be estimated along with

the 95% credible interval.

Data from all patients who receive any study drug will be included in the safety analyses. Patients who entered the study and did not take any of the study drugs and had this confirmed will not be evaluated for safety. The severity of the toxicities will be graded according to the NCI CTCAE v4.0 whenever possible. We will follow standard reporting guidelines for adverse events. Safety data will be summarized by category, severity and frequency. The proportion of patients with AEs will be estimated, along with the Bayesian 95% credible interval. Kaplan-Meier method will be used to assess the overall survival (OS) and progression-free survival (PFS) probabilities. The change of biomarkers over time will be assessed through fitting linear or non-linear mixed effect models.

This study will be conducted as described in this protocol, except for an emergency situation in which the protection, safety, and wellbeing of the patient requires immediate intervention, based on the judgment of the investigator or his/her designee. In the event of a significant deviation from the protocol, the investigator will notify the MDACC surveillance committee following the institutional guidelines.

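### Toxicity is monitored only on the two cohorts pooled, so an excess in one cohort can be largely masked by the other, and Table 14.6 shows only a common rate

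*Combined protocol and SAP*

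**What the plan says.** Section 14.0 sets response futility separately for relapsed/refractory patients (cohort 1, Tables 14.1 and 14.2) and untreated patients (cohort 2, Tables 14.3 and 14.4), with up to 24 in each. Toxicity is handled differently. One rule "will be implemented for toxicity monitoring for patients enrolled in cohorts 1 and 2, where toxicity is defined as any grade 3 or higher" non-hematological event at least possibly related to treatment.

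With a beta(0.6, 1.4) prior, enrolment stops if there is "more than 92% chance that the toxicity rate is more than 30"%. On timing: "The toxicity monitoring rule will be applied starting from the 6th patient, and then in cohort size of 6". Table 14.5 is captioned "Toxicity stopping boundaries in cohort size of 6 for patients enrolled in cohorts 1 and 2" and its last row is at 42 patients, so it can only refer to the combined count ("A maximum of 48 patients will be enrolled in this Phase II study"). Table 14.6 gives stopping probabilities and average numbers treated for true rates of 0.1 to 0.5, each applied to everyone.

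No toxicity boundary is given for a single cohort. The safety summaries in the Analysis Plan are not described as split by cohort. The protocol abstract lists a data safety monitoring board as not applicable.

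**The concern.** The plan treats the two populations as different enough to need separate response targets and separate futility boundaries, but assumes one toxicity rate for both. If toxicity differs, the pooled count averages the two rates, and a cohort well above the 30% threshold can be offset by one well below it. Table 14.6 cannot show this, because every row assumes equal rates. Its 0.93 chance of stopping at 50% toxicity applies only when both cohorts are at 50%.

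At stake is enrolment continuing, often to the full 24, in a cohort whose toxicity the plan itself would call unacceptable. The pooled rule is the only formal group-level safety stop, and no monitoring board is assigned that might look at the cohorts separately.

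**Working it through.** **Inputs (Section 14.0).** Prior beta(0.6, 1.4); threshold 0.30; cutoff 0.92; looks at 6, 12, 18, 24, 30, 36 and 42; maximum 48 (24 + 24).

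**Step 1: reproduce the plan.** After x toxicities in n patients the posterior is beta(0.6 + x, 1.4 + n − x). The boundary is the smallest x with Pr(p > 0.30) > 0.92. At n = 6, x = 4 gives beta(4.6, 3.4) with tail 0.945, and x = 3 gives beta(3.6, 4.4) with tail 0.800, so the boundary is 4. Repeating this at each look gives 4, 7, 9, 11, 13, 15 and 18, exactly Table 14.5. An exact binomial recursion over the looks, with N = 48, one common rate and no futility stop, gives:

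| True rate | Stop, recomputed | Stop, stated | Average N, recomputed | Average N, stated |
|---|---|---|---|---|
| 0.1 | 0.0013 | 0.001 | 47.9 | 47.9 |
| 0.2 | 0.024 | 0.02 | 47.1 | 47.1 |
| 0.3 | 0.187 | 0.19 | 42.3 | 42.3 |
| 0.4 | 0.606 | 0.61 | 30.5 | 30.5 |
| 0.5 | 0.927 | 0.93 | 18.2 | 18.2 |

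Both tables are correct for what they describe.

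**Step 2: unequal rates under the pooled rule.** Take 50% in one cohort and 10% in the other. The mean rate is (0.50 + 0.10)/2 = 0.30, so at 42 patients about 42 × 0.30 = 12.6 toxicities are expected against a boundary of 18. If patients arrive from either cohort with equal chance, each is in effect a draw at 30%, so the plan's own 30% row (0.19) nearly gives the answer. Simulation gives about 0.19. With strictly alternating cohorts the count varies less, and the figure is about 0.14, with about 22 of 24 patients entering the toxic cohort. Accrual mix matters: if the tolerable cohort accrues faster, at 70:30, the chance is about 4% to 5%; if the toxic cohort does, about 46% to 47%.

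**Step 3: add a check within each cohort.** Keep the pooled rule and apply 4/6, 7/12 and 9/18 inside each cohort as well. As a hand check of the first look at 50% toxicity: Pr(X ≥ 4 of 6) = (15 + 6 + 1)/64 = 0.34. Over the three looks a 24-patient cohort closes with probability 0.66. Closure of the toxic cohort, by either rule:

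| Toxicity (one cohort / other) | Pooled only | Pooled plus per-cohort |
|---|---|---|
| 50% / 10% | 14% to 19% | about 66% |
| 50% / 20% | about 36% | about 69% |
| 40% / 20% | about 18% | about 38% |

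At 50%/10% with alternating accrual, average enrolment in the toxic cohort falls from about 22.0 to 14.8, a difference of 22.0 − 14.8 = 7.2. Closure of the tolerable cohort falls from about 14% to 7%, because a pooled stop closes both.

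**Step 4: the price.** Chance of closing at least one cohort:

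| Common toxicity rate | Pooled only | Pooled plus per-cohort |
|---|---|---|
| 20% | 2.4% | about 5.5% (5.2% to 5.5% across runs) |
| 30% | 18.5% | about 27% |

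Counted per cohort the rises are smaller (2.4% to about 4%, and 18.6% to about 23%), but the trial-level figures are the ones to disclose.

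**Step 5: Table 14.6 and futility.** From Tables 14.2 and 14.4, the chance that futility closes at least one cohort is 1 − (1 − 0.14)(1 − 0.16) = 0.28 at the target response rates (30%/50%), and 1 − (1 − 0.14)(1 − 0.78) = 0.81 if both are 30%. With both rules running and each futility stop closing only its own cohort:

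| Response (cohort 1 / 2) | Stop for toxicity at 30% / 40% / 50% |
|---|---|
| Table 14.6 as stated | 0.19 / 0.61 / 0.93 |
| 30% / 50% (targets) | 0.18 / 0.60 / 0.92 |
| 30% / 30% | 0.18 / 0.55 / 0.88 |
| 10% / 30% | 0.15 / 0.47 / 0.79 |

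At 10% toxicity, average N is about 44.7 at the targets (Tables 14.2 and 14.4 give 22.6 + 22.2 = 44.8) and about 28.5 at 10%/30%, against 47.9 stated.

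**Assumptions.** Outcomes are known at each look, and toxicity and response are independent. Steps 2 to 4 ignore futility. Simulations used 15,000 to 40,000 trials per case.

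**The case against.** Pooling is defensible. Both cohorts receive the same regimen, the study is small, and nothing in the documents predicts a five-fold difference in toxicity. At a common 40% rate the pooled rule stops with probability 0.61, against 0.34 for the same rule in one 24-patient cohort. That argues against replacing the pooled rule, but not against adding to it: with both in place, closure of a given cohort at a common 40% goes from about 0.60 to about 0.63.

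The 50%/10% case is severe, and masking is weaker for milder contrasts: at 50%/30% the pooled rule stops about 60% of the time. This stands as a limit on size. At 40%/20%, however, the pooled rule still stops only about 18% of the time.

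A reader might infer that a toxic cohort would go unnoticed. The documents do not support that. The dose delay and discontinuation rules (Section 6.0), serious adverse event reporting (Section 11.1.5) and monitoring by the IND Office all apply whatever the cohort. None of them is a cohort-level stop to enrolment, so the gap is in the formal rule.

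A reader might also infer that Table 14.6 is wrong because futility will usually keep enrolment below 48. At the plan's own targets that happens in about 28% of trials, and the stopping probabilities barely move. It becomes usual only if response falls short. Response is also scored over 6 months, accrual is estimated at 1 to 2 patients a month, and no accrual pause is stated. So 6 to 12 patients could enter while one response is awaited, and futility would shorten enrolment less than these calculations assume. Tabulating each rule alone is a presentation choice, which Tables 14.2 and 14.4 share.

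**Conclusion.** The point holds as a gap in the design, not as an error of calculation. The only formal toxicity rule can largely mask an excess confined to one cohort: it stops about 14% to 19% of the time at 50%/10%, about 36% at 50%/20% and about 18% at 40%/20%. Adding boundaries the plan already contains raises closure of the toxic cohort to about 66%, 69% and 38%.

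The Table 14.6 point is secondary and mainly one of labelling. The omission of futility matters little at the target response rates and becomes large only if response is well below target, or if one cohort's futility stop closes the whole study. On that second reading the stopping probabilities at the targets are 0.17, 0.55 and 0.87 at 30%, 40% and 50% toxicity. Section 14.0 speaks of stopping the trial while setting the futility rule per cohort, so the documents do not settle which reading applies.

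All figures for unequal rates depend on accrual order and on outcomes being available at each look.

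**What to change.** 1. Keep the pooled rule. Add that the first three rows of Table 14.5 (4/6, 7/12, 9/18) also apply within each cohort, and that crossing one closes enrolment to that cohort only.
2. State the trial-level cost beside it: at least one cohort closed in about 5.5% of trials rather than 2.4% when both rates are 20%, and about 27% rather than 18.5% when both are 30%. If that is judged too high, at least report the pooled rule's behaviour under unequal rates, so that the choice is explicit.
3. Label Table 14.6 as assuming 48 patients, one common rate and no futility stop. Add rows for unequal rates and for both rules running together, at the target response rates and at lower ones.
4. State whether a futility stop closes one cohort or the whole study.

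The work is a short simulation, a few sentences and some added table rows. Sample size and the existing boundaries do not change. The real cost is the higher chance of a false cohort closure given in item 2.
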